Visit Window (±Days)	±3	±7	±7 (See Note)	±7 (See Note)	±7	±7	±7	±7	±7	Note: For the EOP visit only (Month 6 or Month 9/EOP, as appropriate), the window for audiological/BAEP central read (including any repeat assessments if deemed necessary by the central reader) is -7/+21 days. All other assessments, including the primary audiological/BAEP assessments, must be completed within ±7 days.
Neurological examination by a neurologist			X (see Note)	X			X			Neurological examination will include the Neuropathy Assessment. Refer to the Manuals for General Neurological and Neuropathy Assessments for more information. See Section 8.2.5 . Note: Assessment at Month 6 is required only for those eligible participants who enter the active therapy extension phase at Month 6 (See Section 4.1).
Vital signs	X	X	X	X	X	X	X	X	X	See Section 8.2.2 .
12-lead ECG			X (see Note)	X					X	See Section 8.2.4 . Note: Assessment at Month 6 is required only for those eligible participants who enter the active therapy extension phase at Month 6 (See Section 4.1).

Procedure	Intervention Period									Notes
	TP1: Placebo-controlled Phase				TP2: Active Therapy Extension Phase					
Visit Identifier	3	4	5	6	7	8	9	10	11	Visit 6 (Month 9/EOP), the last visit of the placebo-controlled phase, is also the first visit of the active therapy extension phase.
Visit (Months)	1	3	6	9 / EOP	3E	6E	9E	12E	15E	E=Active Therapy Extension Phase Note: Those participants who enter the active therapy extension phase at Month 6 (Visit 5) are to complete at that visit all Month 6 (Visit 5) assessments and then follow the schedule of visits in the active therapy extension phase starting with Month 3E,
Day	31	91	181	271	91E	181E	271E	361E	451E	Day relative to the start of the study phase (ie, Day 1 = start of Placebo-controlled Phase; Day 1E = start of Active Therapy Extension Phase).
Visit Window (±Days)	±3	±7	±7 (See Note)	±7 (See Note)	±7	±7	±7	±7	±7	Note: For the EOP visit only (Month 6 or Month 9/EOP, as appropriate), the window for audiological/BAEP central read (including any repeat assessments if deemed necessary by the central reader) is -7/+21 days. All other assessments, including the primary audiological/BAEP assessments, must be completed within ±7 days.
Weight			X (see Note)	X					X	Note: Assessment at Month 6 is required only for those eligible participants who enter the active therapy extension phase at Month 6 (See Section 4.1).

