8.2.7. Brainstem Auditory Evoked Potential Evaluations

All participants will have a BAEP evaluation, as specified in the Manual for BAEP Evaluation, at the times specified in the SoA (Section 1.3). When possible, the participant should have the evaluations performed at the same evaluation center, by the same audiology professional using the same equipment, during the study. Audiology and BAEP evaluations should be done on the same day, with audiology assessment first. If they cannot be done on the same day, assessments must be within 7 days of each other.

A central reader will be used for BAEP to confirm that locally read BAEP waves were labelled appropriately and at their peak so that latency and amplitude data are accurate. Central reading will also ensure consistency in BAEP interpretation. The BAEP recording may be repeated (including additional recordings with modified parameters) or the original recording may be reassessed based on feedback from the central reader. Only results confirmed by the central reader as accurately interpreted will be used for analysis.

For participants who terminate early from the study, the BAEP evaluation should be performed.

For follow-up assessment of participants who discontinue due to an auditory adverse event see Section 10.7.

Refer to the most current version of the Manual for BAEP Evaluation for details on BAEP evaluation.

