**Table 4. Groups**

Period	Groups
Placebo-controlled phase (TP1)	
 
• Ritlecitinib 200/50 mg QD
 
• Placebo
 

Active therapy extension phase (TP2)	
 
• Ext Ritlecitinib 50 mg QD
 
• Ext Ritlecitinib 200/50mg QD
 

Overall (TP1+TP2+TP3+Observation period)	
 
• Ritlecitinib 200/50/50 mg QD
 
• Any Ritlecitinib
 
• Any Ritlecitinib + Placebo (Total)
 

- For all the other tables, groups will be:
  - Ritlecitinib 200/50/50 mg QD
  - Placebo → Ritlecitinib 200/50 mg QD.

### 8.3. Supplemental CSR 2

The supplemental CSR 2 will be focused on safety and efficacy data from TP3 and will be prepared after the last participant completes the last visit or discontinues from the study.

- Disposition date of TP2 (or of 4 weeks follow-up period if participants didn't enter TP3) will be used to identify records in TP2 and TP3.
- All safety data in TP3, regardless of whether participants are in the Observation Period or not, will be included in summary tables.
- Only one group “All participants” including all participants will be used in all summaries.
- Efficacy data of participants while in the Observation Period will not be included in summary tables that present TP3 data by visit. Instead, listings and plots may be provided.

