## 11. APPENDICES

### 11.1. Appendix 1 Definition and Use of Visit Windows in Reporting

Visit windows will be used for efficacy variables and for any safety data that are displayed or summarized by study visit.

Visit Label	Target Day	Analysis Visit Window
Baseline	1	Up to Day 1
Month 1	31	Days 2 to 60
Month 3	91	Days 61 to 136
Month 6	181	Days 137 to 226 but <=Day 1E
Month 9	271	Days 227 to 316 but <=Day 1E
Month 3E	91E	Days 2E to 136E
Month 6E	181E	Days 137E to 226E
Month 9E	271E	Days 227E to 316E
Month 12E	361E	Days 317E to 406E
Month 15E	451E	Day 407E to 541E
Month 21E	631E	Day 542E to 721E
Month 27E	811E	Day 722E to 901E
Month 33E	991E	Day 902E to 1081E
Month 39E	1171E	Day 1082E to 1261E
Month 45E	1351E	Day 1262E to 1441E
Month 51E	1531E	Day 1442 to last dose + 14 days
28-Day Follow-up	28 days after last dose	Based on nominal visit
6-Month Follow-up	182 days after discontinuation	Based on nominal visit

E=relative day to the first dose at active therapy extension phase.

If more than one observation falls within a visit window, the observation that is the closest to the target date for that visit will be used for the summary tables. If two visits are equally distant from the target day, the data from the later visit will be used.

Data collected in TP2, from the first dose in TP2 till the end of follow-up or the first dose in TP3, will be used to derive analysis visits in TP2. Data collected in TP3, from the first dose in TP3 or the Observation Period will be used to derive analysis visits in TP3.

Some endpoints (eg, BAEP) are not scheduled to be assessed at each visit and some measurement may fall outside the scheduled visit windows. In this case, for variables where mixed model methodology is used, the data from the unscheduled 'windowed' visits will not be included in mixed model analysis. However, these visits will be summarized descriptively in the observed cases analysis, using the visit timepoint corresponding to their actual visit window (for example a participant with a visit on Day 59 will be summarized at Month 1 in the observed case summaries).

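### SAP Appendix 1 contradicts itself at the TP2/TP3 boundary, so a Month 15E BAEP or biopsy obtained after the first TP3 dose can be left without an analysis visit

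*SAP*

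**What the plan says.** SAP 11.1 (Appendix 1) assigns records to visits by two rules.

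- **Day rule (the table).** Month 15E, the last TP2 visit, has target 451E and window "Day 407E to 541E". Month 21E, the first TP3 visit, has "Day 542E to 721E". The Month 15E row has no cap at the next phase. The rows that end the placebo phase do; Month 9, for example, reads "Days 227 to 316 but <=Day 1E".
- **Phase rule (the text below the table).** TP2 visits use "Data collected in TP2, from the first dose in TP2 till the end of follow-up or the first dose in TP3". The next sentence says "Data collected in TP3, from the first dose in TP3 or the Observation Period will be used to derive analysis visits in TP3".

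The protocol lets Month 15E data arrive late. BAEP and audiology may be done on different days, up to 7 days apart (schedule 1.3.2.1; 8.2.7). The central reader may prompt a repeat recording, and "Only results confirmed by the central reader as accurately interpreted will be used for analysis" (8.2.7). In a public emergency, the Month 15E special safety assessments may run to Day 481E (Appendix 9, Table 4). Missed BAEPs and biopsies are then due at the next opportunity, even outside the window (10.9.3.3, 10.9.3.4).

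At the end of the placebo phase, next-phase drug is not dispensed until BAEP, central read and any repeats are complete (schedule 1.3.2.1; 6.2.1). The matching extended window is limited: "For the EOP visit only (Month 6 or Month 9/EOP, as appropriate), the window for audiological/BAEP central read". The emergency hold in 10.9.4 covers Month 9 only. For Month 15E, the TP3 schedule (1.3.2.2) says that entrants complete all assessments at that visit and that IRT is contacted then for TP3 assignment. It does not tie the first TP3 dose to a completed central read, repeat or late biopsy.

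**The concern.** The table places a record from, say, Day 465E in Month 15E. The phase sentence bars it from Month 15E if the participant has taken a TP3 dose, and Month 21E has not yet opened. Two programmers could follow the same appendix and report different Month 15E counts.

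Month 15E is the last scheduled BAEP and biopsy time point, so no later scheduled value can stand in. Safety summaries use observed data (Protocol 9.4.3), so a record with no visit drops out of the by-visit table. Suppose the first recording is missing or not centrally confirmed, and the valid one follows the first TP3 dose. That participant then has no Month 15E value. Whether the value survives depends on entry to TP3 rather than on the measurement.

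**Working it through.** **Inputs.** Target days 361E, 451E and 631E, the windows and the phase rule come from SAP 11.1. The ±7-day visit window is in Protocol 1.3.2.1, and the emergency limit of Day 481E is in Protocol Table 4. The documents do not give the day of the first TP3 dose. I assume it is at or just after the Month 15E visit and vary it.

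**1. Reproduce the plan's windows.** Edges are midpoints between target days.
- (361 + 451)/2 = 406, so Month 15E starts at 407E.
- (451 + 631)/2 = 541, so Month 15E ends at 541E and Month 21E starts at 542E.

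Both match the SAP.

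**2. Apply the day and phase rules together.** For a first TP3 dose on day D, counting D itself, the unassigned days run from D to 541E. Their number is 541 − D + 1.

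| First TP3 dose | Unassigned days | Number |
|---|---|---|
| 444E | 444E–541E | 98 |
| 451E | 451E–541E | 91 |
| 452E | 452E–541E | 90 |
| 458E | 458E–541E | 84 |

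**3. Test individual days, with the first TP3 dose on 451E or 452E.**

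| Record on | Both rules, TP3 entrant | Table alone | Non-entrant |
|---|---|---|---|
| 455E, 458E, 465E | no visit | Month 15E | Month 15E |
| 481E | no visit | Month 15E | Month 15E if follow-up has not ended |
| 542E | Month 21E | Month 21E | not applicable |

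For a non-entrant whose last dose is on 451E, follow-up falls at 451 + 28 = 479E, ±7 days, so 472E to 486E.

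**4. Which permitted records can land in the gap?**
- *BAEP on a different day from the visit:* up to 7 days after audiology, for example audiology on 451E and BAEP by 458E.
- *BAEP repeat on central-reader feedback:* 8.2.7 does not restrict this to the end of the placebo phase.
- *BAEP or biopsy delayed by a public emergency:* to 481E, which is 481 − 451 = 30 days after target, or later at the next opportunity.

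**5. When is a value actually lost?** Three things must coincide: no usable recording before the first TP3 dose, a valid one after it but by 541E, and the phase sentence applied as written. A participant with a confirmed pre-dose recording keeps a Month 15E value.

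**6. Effect on precision, by assumption only.** The plan's SD of 0.2 ms and 30 per group give 1.96 × 0.2/√30 = 0.072 ms (the plan states 0.07). If as many as 9 of 30 were lost, 1.96 × 0.2/√21 = 0.086 ms. The range of 0 to 9 lost is mine; the documents give no rate.

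**The case against.** The best defence is that the appendix already points to the sensible answer. The Month 15E row is uncapped, although the SAP wrote caps where it wanted them. A later paragraph in Appendix 1, which names BAEP, says measurements outside scheduled windows are summarised descriptively at the visit whose window contains them. Month 15E BAEP is only ever summarised descriptively. BAEP and biopsy are not scheduled in TP3, so a late Visit 11 recording could be regarded as TP2 data. Entrants are also told to complete everything at the visit, so late records should be few.

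Most of this stands as evidence of intent, and it shows that data loss is not certain. It does not remove the conflict. The later paragraph does not waive the phase sentence, and that sentence defines TP2 data by dosing dates, not by the visit a recording was meant for. The instruction to complete assessments at the visit is not a hold on the first TP3 dose.

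A reader might also infer that the ordinary +7-day visit window loses data. It does not: a visit on 458E moves TP3 assignment with it. Nor do the documents support reader-requested repeats for biopsy. Those are described for BAEP only; for biopsy, only the emergency delay applies.

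**Conclusion.** The conflict is real but narrow. Applied as written, Appendix 1 leaves 84 to 98 days with no analysis visit for a TP3 entrant, assuming the first TP3 dose falls on Days 444E to 458E. Late or repeat BAEP and late biopsy records allowed by the protocol can fall there. What is at stake is the completeness of the descriptive secondary Month 15E BAEP and biopsy summaries in supplemental CSR 1. No hypothesis is tested on them, and the Month 9 primary analysis is unaffected.

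Two stronger readings are tempting and unsupported. First, the width of the gap might be turned into a count of lost participants. It measures calendar days, and the documents give neither TP3 uptake nor a repeat rate. The central reader may also have the original recording reassessed, which creates no new date. Second, SAP 8.3 separates phases differently, by a TP2 disposition date that "will be used to identify records in TP2 and TP3". A reader might infer that this also drops these records. That section governs supplemental CSR 2, which contains no BAEP or biopsy endpoint.

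**What to change.** Add one sentence to SAP Appendix 1: BAEP and skin-biopsy records on Days 407E to 541E are assigned to Month 15E whether or not the first TP3 dose has been taken, since neither is scheduled in TP3. The existing nearest-to-target rule still chooses among several usable records.

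Keep the first-TP3-dose boundary for adverse-event risk periods and for assessments that continue in TP3, such as laboratory tests, vital signs and SALT. Extending the exception to those would label TP3 records as Month 15E. SAP 8.3 needs no change for these endpoints, and dispensing rules are not touched.

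The cost is one sentence and a small programming change, with no new data. The downside is that a few Month 15E values would be recorded days to weeks after TP3 supply begins, at the same planned dose. A footnote giving the number of such values would make this visible.

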### 11.2. Appendix 2 List of Countries by Region

Region	Countries
North America	Canada, United States
Europe	Poland
Rest of World	Australia, Argentina, Chile, Colombia, Mexico

**11.3. Appendix 3 Study Days Used to Define Each Visit Period in the Calculation of By Visit Table for Compliance.**

Month 1: Day 1 – Day 31

Month 3: Day 32 to Day 91

Month 6: Day 92 to Day 181

Month 9: Day 182 to Day 1E -1

Month 3E: Day 1E to Day 91E

Month 6E: Day 92E to Day 181E

Month 9E: Day 182E to Day 271E

Month 12E: Day 272E to Day 361E

Month 15E: Day 362E to Day 451E

Month 21E: Day 452E to Day 631E

Month 27E: Day 632E to Day 811E

Month 33E: Day 812E to Day 991E

Month 39E: Day 992E to Day 1171E

Month 45E: Day 1172E to Day 1351E

Month 51E: Day 1352E to Day 1531E
